## I .Test background

Depression is an important cause of global disability and mortality, and its prevalence continues to rise. Compared with the general population, the incidence of depressive symptoms in patients with thyroid cancer is high. The psychological survey of thyroid cancer patients after thyroid cancer surgery found that the number of positive symptom self-rating scale, depression, anxiety and terror factors, and pessimism factors in the thyroid cancer postoperative group were higher than those in the control group. In modern society, the acceptance of mental diseases such as depression is generally low. Patients with depression often do not choose to seek medical treatment because of their stigma and lack of understanding of mental illness. As a result, many patients miss the best treatment opportunity because they do not get timely and accurate diagnosis.

Due to the characteristics of multi-component, multi-target, dynamic and holistic in the research of traditional Chinese medicine, it is necessary to continuously develop new strategies to study the therapeutic mechanism of active components of traditional Chinese medicine. Metabonomics combined with intestinal metagenomics, metagenomics and other multi-omics platforms can jointly identify new functional metabolites and functional bacteria, laying a good foundation for the study of the mechanism of active ingredients related to traditional Chinese medicine. It has been found that the composition and function of intestinal microorganisms in patients with depression are imbalanced. Imbalanced microbiota may induce depression and anxiety through the microbial-gut-brain axis ( biosynthesis and metabolic pathways of tryptophan ). It may also be involved in the occurrence of depression through other flora metabolites ( amino acids, fatty acids, short-chain fatty acids, etc. ). Therefore, this study used the wall-removed Ganoderma lucidum spore powder to intervene in patients with thyroid papillary carcinoma accompanied by depressive symptoms, and explored the antidepressant mechanism of the wall-removed Ganoderma lucidum spore powder through microbial 16 s diversity analysis and metabolomics methods.

Ganoderma lucidum spores are rich in polysaccharide peptides, adenine

---

nucleosides, proteins, enzymes, trace elements and other special components. The key effective components known now are Ganoderma lucidum polysaccharides and Ganoderma lucidum triterpenes. Ganoderma lucidum is widely used as a medicinal fungus to prevent and treat many diseases. Studies have shown that Ganoderma lucidum spore powder has antidepressant effect.

This study was carried out only in this research institution. A total of 300 patients with papillary thyroid carcinoma accompanied by depressive symptoms were recruited to participate in this clinical study. This study was divided into study group and control group, ratio ( 2 : 1 ). From the first day, the experimental group was given oral administration of 4g of Ganoderma lucidum spore powder ( 1 bag at a time, 2 times a day, 2g / bag ) for 90 days, and the control group was given oral administration of 4g ' placebo ' ( 1 bag at a time, 2 times a day, 2g / bag ) for 90 days. Ganoderma powder product instructions : daily care dose is 2g / d, 4g / d can achieve the therapeutic effect. In the previous study, ' wall-removing Ganoderma lucidum spore powder ' was used in clinical practice, prevention and reduction of cancer-related fatigue symptoms in cancer patients, and improvement of the quality of life of cancer patients in the Second Zhejiang Hospital. Ganoderma lucidum medication method 2g / time, once in the morning and once in the evening, a total of 4g. The same dose was used.

## **II.test purpose**

1. In this study, the antidepressant mechanism of ganoderma lucidum spore powder was studied by microbial 16 s diversity analysis and metabolomics method, and the clinical efficacy of ganoderma lucidum spore powder intervention on postoperative depressive symptoms of papillary thyroid carcinoma was determined.
2. To investigate the effect of Ganoderma lucidum spore powder on the depression of patients through the communication pathway of microbial-intestinal-brain axis ( biosynthesis and metabolic pathway of tryptophan ), or through other microbial metabolites ( amino acids, fatty acids, short-chain fatty acids, etc. ) to inhibit the occurrence of depression in patients. To clarify the antidepressant mechanism of

---

wall-removed Ganoderma lucidum spore powder and provide objective basis for its application.

[figure not shown]
3. To construct a clinical database of patients with depressive symptoms after papillary thyroid carcinoma surgery, and to explore the optimal mode of intervention of exfoliated ganoderma lucidum spore powder in patients with depressive symptoms.

The multi-omics platforms such as metabolomics and intestinal flora were used to directly find the functional components related to the intervention effect of wall-removed Ganoderma lucidum spore powder ; combined with clinical data, mining potential clinical indicators or more sensitive biomarkers ; on this basis, the in vivo function and mechanism of the target flora ( potential metabolic beneficial bacteria ) or metabolites ( potential epigenetic or parabiotic ) alone or in combination will be verified.

### **III.experimental design**

1. design description: A randomized, double-blind, parallel, placebo-controlled study.

2. technical route

---

## IV.case selection

### 4.1 inclusion criteria

- ( 1 ) Patients with depressive symptoms after papillary thyroid carcinoma surgery in the outpatient department of Zhejiang Cancer Hospital ( patients with depressive symptoms by clinical psychiatrist and Hamilton Depression Scale score of 8-20 points ) ;
- ( 2 ) Han nationality ;
- ( 3 ) no previous depression and other mental diseases ;
- ( 5 ) 18-80 years old ;
- ( 6 ) Women ;
- ( 8 ) BMI : 19 ~ 24. ( BMI calculation method :  $BMI = \text{weight ( kg )} / \text{height}^2$  ( m ) )

### 4.2 excluded criteria

- ( 1 ) suffering from other diseases of the intestinal system ;
- ( 2 ) Have received gastrointestinal surgery before intervention ;
- ( 3 ) Including patients with other malignant tumors, who need chemotherapy, radiotherapy, biological therapy or traditional Chinese medicine treatment ;
- ( 4 ) received antibiotics or microecological modulators within 3 months before the intervention ;
- ( 5 ) Acute intestinal obstruction ;
- ( 6 ) Patients with severe depressive symptoms who must receive antidepressant treatment ;
- ( 7 ) organic diseases such as heart and brain diseases, brain trauma ;
- ( 8 ) history of mental illness, use of psychoactive drugs such as drugs ;
- ( 9 ) Severe liver and kidney dysfunction ;
- ( 10 ) Pregnancy, lactation

### 4.3 rejecting standard

- ( 1 ) After enrollment, it was found that the included objects did not meet the inclusion criteria ;

---

( 2 ) Subjects who did not take oral ganoderma lucidum spore powder or intervene in the course of dissatisfaction after enrollment according to the study protocol ;

( 3 ) poor compliance, midway active withdrawal or lack of main indicators, incomplete data, etc., can not determine the efficacy or safety.

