## **X. Statistical analysis of test data**

### **1. Data Selection for Statistical Analysis**

( 1 ) Full Analysis Set ( FAS ) : Constituted of all cases with depressive symptoms after papillary thyroid carcinoma surgery that were randomized into groups and at least 1 month after surgery, that is, Intention-to-treat. The FAS set was used for efficacy analysis, and the missing data was filled with the last observed data filling ( LOCF ) criterion.

( 2 ) Per-Protocol Set ( PPS ) : PPS is composed of all cases that meet the test plan, have good compliance, do not use prohibited drugs during the test, and complete the content of CRF requirements. The PPS set is used for efficacy analysis.

( 3 ) Safety Analysis Set ( SAS ) : It is composed of all cases that have been randomly grouped, used at least one drug and have safety evaluation. The SAS set is used for safety analysis.

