### **2. statistical analysis plan**

---

Statistical analysis was performed using SPSS 9.1.3 statistical software.

( 1 ) Distribution of two groups of cases : the comparison of the shedding and elimination rates of the two groups was performed by  $\chi^2$  test or exact probability method.

( 2 ) Comparability analysis : Demographic data and other basic indicators were compared to measure the comparability of the two groups. According to the type and distribution of data,  $\chi^2$  test or exact probability method, CMH test, t test, variance analysis or non-parametric statistical method were used.

( 3 ) Compliance analysis : To compare whether the two groups of patients use the test drugs on time and in quantity. The drugs that were not banned in the regimen were mainly tested by  $\chi^2$  test or exact probability method.

( 4 ) Validity analysis : Repeated measures were used to compare the differences in measurement data such as depression scores and sleep scores between the experimental group and the control group, or linear regression models were used to control baseline depression scores or sleep scores. Differences in depression scores and sleep scores between the two groups. Compare the score after the end of the experiment with the baseline score, calculate the difference before and after the change, and use the t test to compare the difference between the score changes of the experimental group and the control group.

( 5 ) Safety analysis : adverse reactions were statistically described, and the incidence of adverse reactions in the two groups was compared by  $\chi^2$  test or exact probability method.

( 6 ) All statistical tests should give test statistics and corresponding p values. When using the exact probability method, the p value is given directly.  $P \leq 0.05$  indicated that the difference was statistically significant.

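### Section 4.3 rejects enrolled patients for non-adherence, withdrawal or missing data without saying from which analysis set, and X.1 names no primary efficacy set

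*Combined protocol and SAP*

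**What the plan says.** Section 4.3 (rejecting standard) gives three grounds, all applied after enrolment:

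1. Ineligibility discovered late: "After enrollment, it was found that the included objects did not meet the inclusion criteria".
2. Product not taken or, as I read a garbled phrase, course not completed: "Subjects who did not take oral ganoderma lucidum spore powder or intervene in the course of dissatisfaction after enrollment according to the study protocol".
3. Adherence, withdrawal and missing data: "poor compliance, midway active withdrawal or lack of main indicators, incomplete data, etc., can not determine the efficacy or safety".

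No analysis set is named there. The section also does not say who decides on rejection, when, or whether blind to arm.

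Section X.1 (Data Selection for Statistical Analysis) defines the sets. The FAS is "Constituted of all cases with depressive symptoms after papillary thyroid carcinoma surgery that were randomized into groups and at least 1 month after surgery", and it is labelled intention-to-treat. That definition contains no adherence or completion condition. On its use: "The FAS set was used for efficacy analysis, and the missing data was filled with the last observed data filling". The PPS consists of compliant cases with complete records and no prohibited drugs, and it too is used for efficacy. Neither set is called primary.

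Section X.2(1) plans a test for "the comparison of the shedding and elimination rates of the two groups", so elimination is a case status that will be counted by arm. It is not linked to either set.

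**The concern.** The two sections can give different answers for the same randomized patient. Someone who withdraws midway and has no D90 HAMD-24 falls within the wording of 4.3(3). Under X.1(1) the same person belongs in the FAS with an earlier score carried forward. Nothing in the plan says which section governs.

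Adherence, withdrawal and availability of the outcome all arise after randomization. Patients may stop for lack of benefit or for discomfort, and both can depend on the arm. Removing them from the efficacy comparison gives up the protection of randomization and draws the FAS towards the PPS. Because X.1 uses both sets for efficacy without ranking them, a result in adherent completers could become the headline even if the FAS is kept intact.

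**Working it through.** **The plan's own figure.** Section 5.1 starts from 100 pairs and allows 15% shedding: 100 / (1 − 0.15) = 117.65. The stated 117 pairs is this value truncated (rounding up gives 118), so it reproduces. It has no bearing on the present point except as the source of the 15%. Section 5.1 gives no effect size, SD or power.

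**The passages side by side.**

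| Randomized patient | Section 4.3 | FAS, X.1(1) | PPS, X.1(2) |
|---|---|---|---|
| Found ineligible after enrolment | Rejected | No exclusion stated, if within the FAS definition | Out |
| Did not take the product or complete the course | Rejected | In | Out |
| Poor compliance | Rejected, perhaps only if not evaluable | In | Out |
| Withdrew, or main indicator missing | Rejected, perhaps only if not evaluable | In, last score carried forward | Out |

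The 4.3 column agrees with the PPS column and conflicts with the FAS column. The text does not say which pairing is meant.

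**Size of the efficacy set.** Inputs are 200 and 100 patients (Section 5.1) and an assumed 15% rejection in each arm. The 15% borrows the shedding rate, because the plan gives no rejection rate.

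- FAS as written: 200 + 100 = 300.
- With 4.3 applied first: 200 × 0.85 = 170 and 100 × 0.85 = 85, total 255.
- Standard error ratio: √(1/0.85) = 1.085.
- Difference detectable with 80% power, two-sided 0.05 (sidedness is not stated), is (1.960 + 0.842) × √(1/n_E + 1/n_C). This is 0.343 SD at 200/100 and 0.372 SD at 170/85.
- At an assumed true effect of 0.35 SD, power is 81.5% and 75.0% respectively.

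The figures for 300 are nominal, since they count carried-forward scores as full observations.

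**Bias if rejection differs by arm.** Assume no true effect among all randomized patients, and rejected patients g SD worse than retained ones in both arms. The retained mean in an arm with rejection rate r exceeds that arm's full mean by g × r. Hence bias = g × (r_E − r_C), and a positive value favours the spore powder. Type I error uses the normal approximation with SE = √(1/[200(1 − r_E)] + 1/[100(1 − r_C)]). Every scenario keeps overall rejection at 15%, for example (200 × 0.20 + 100 × 0.05)/300 = 0.15.

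| r_E / r_C | Bias in SD at g = 0.25, 0.5, 1.0 | Two-sided type I error |
|---|---|---|
| 15% / 15% | 0, 0, 0 | 5.0%, 5.0%, 5.0% |
| 17.5% / 10% | 0.019, 0.0375, 0.075 | 5.2%, 5.9%, 8.8% |
| 20% / 5% | 0.0375, 0.075, 0.15 | 6.0%, 8.9%, 21.2% |
| 10% / 25% | −0.0375, −0.075, −0.15 | 5.9%, 8.5%, 19.4% |

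The values of g and the arm-specific rates are assumptions chosen to show a range; none comes from the plan.

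**The case against.** The strongest reply is that X.1, not 4.3, decides who is analysed. It keeps all randomized cases, and its rule that "the missing data was filled with the last observed data filling ( LOCF ) criterion" would be largely pointless if patients with missing scores had already been removed. The PPS definition closely mirrors 4.3, so 4.3 may simply list PPS exclusions. The closing words of 4.3(3) can also be read as limiting rejection to cases that cannot be evaluated. A patient who stops at week 6 would normally have a D28 HAMD-24 (Section 7.2), so it is not settled that 4.3(3) rejects that patient.

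Much of this stands: the PPS-only reading is coherent and may be what was meant. It is not written, however. Section 4.3 sits under case selection, is separate from the withdrawal rules in 4.4, and refers to safety as well as efficacy, although the PPS is an efficacy set. An analyst who applied it first would be following the text.

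Three stronger inferences are tempting and should not be drawn:

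- **That the trial will be analysed in completers only.** The documents do not show this. The planned test of elimination rates shows that such cases are counted, not that they leave the FAS.
- **That safety data will be lost.** Section IX keeps every user of the test drug in the safety evaluation, evaluable or not. X.1(3) defines the safety set without reference to adherence or completion.
- **That 4.3(2) applies a different rule to each arm because it names only the spore powder.** The sentence is visibly garbled, and Section 5.3 defines the research drugs as spore powder or placebo, so loose drafting is the likelier explanation.

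**Conclusion.** The point holds as an unresolved conflict between 4.3 and X.1, made worse by having two unranked efficacy sets. It is more than a missing detail, because 4.3 applied as worded would remove randomized patients on grounds that arise after randomization and may depend on arm.

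Its size depends on unknowns. At an assumed 15% rejection per arm, 45 of 300 patients are at issue (30 and 15), and the standard error rises by about 8.5%. Bias is zero with equal rates and reasons. In the unequal scenarios shown it runs from about 0.02 to 0.15 SD in either direction, with type I error between 5.2% and 21.2%. The upper end needs both a large imbalance in rejection and a full SD gap between rejected and retained patients, and the plan gives no evidence for or against either.

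**What to change.** - State in 4.3 and X.1 that 4.3 cases are excluded from the PPS only, and that every randomized patient stays in the FAS in the allocated arm. Allow one exception: ineligibility judged blind to arm on data recorded before randomization.
- Name the FAS as the primary efficacy set and the PPS as supportive. Without this, the first change still leaves room for a completers' headline result.
- Report rejections by arm and reason, alongside the comparison of rates already planned in X.2(1).
- Keep collecting the planned D28 and D90 HAMD-24 and PSQI, with consent, from patients who stop the product. Sections 7.2 and 7.3 do not say whether these visits continue for them. This goes beyond wording, but it reduces how much of the FAS rests on carried-forward scores.

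The cost is a few sentences in 4.3 and X.1 and modest follow-up effort. The FAS estimate may be slightly less favourable than one in adherent completers.

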#### 4.4 The subjects withdrew from the test standard

( 1 ) It is necessary for researchers to stop the trial from the perspective of medical ethics ;

( 2 ) patients with severe adverse reactions ( SAE ), complications or special physiological changes should not continue to accept the test ;

( 3 ) Pregnancy during treatment.

### **V.test scheme**

#### 5.1 Number of cases and distribution of cases

According to the ' Drug Registration Management Method ', the study sample should be no less than 100 pairs. It is assumed that the case shedding rate is 15 %, and the sample size is not less than 117 pairs. Finally, the sample size was determined to be 300 cases. In order to reduce the use of placebo in the control group, so that more patients benefit from treatment, the experimental group : the control group was assigned to 2 : 1, that is, 200 cases in the experimental group and 100 cases in the control group.

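### Section 5.1 sets minimums of 100 and 117 pairs, but its 100 controls cannot meet them one-to-one, and no conversion from pairs to 2:1 is given

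*Combined protocol and SAP*

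**What the plan says.** The whole argument for the sample size is in Section 5.1 (Number of cases and distribution of cases). It runs in four steps.

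1. A drug registration rule is cited for a floor: "the study sample should be no less than 100 pairs".
2. The floor is raised for dropout: "It is assumed that the case shedding rate is 15 %, and the sample size is not less than 117 pairs".
3. The total is fixed: "Finally, the sample size was determined to be 300 cases".
4. Allocation is set at 2:1, with the reason "In order to reduce the use of placebo in the control group" and so that more patients receive the active product. The result is "200 cases in the experimental group and 100 cases in the control group".

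Section I repeats the 300 patients and the 2:1 ratio without a derivation. No section defines a pair under unequal allocation or shows how 117 pairs becomes 300 patients. No effect size, standard deviation or power is given in support of the size.

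Two statements in Section X bear on how dropouts are counted. For the full analysis set, "the missing data was filled with the last observed data filling ( LOCF ) criterion". The analysis plan also calls for "the comparison of the shedding and elimination rates of the two groups", so shedding and elimination are separate categories.

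**The concern.** In a two-arm trial a pair ordinarily means one patient from each arm, so 117 pairs would need 117 controls. The paragraph that sets this minimum provides 100. The placebo-sparing reason explains why the ratio is 2:1, but it does not explain how 100 controls satisfy 117 pairs.

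The pair count is the only basis the plan offers for its size. A reader who checks it against the allocation in the same paragraph gets opposite answers depending on what pairs means, and the plan does not say which meaning applies. What is at stake is whether the stated justification supports the design as written.

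**Working it through.** **Inputs, all from Section 5.1:** floor 100 pairs; shedding 15%; inflated minimum 117 pairs; total 300; arms 200 and 100.

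**Reproducing the plan's figure.** Inflation is N/(1 − d) = 100/0.85 = 117.65. The plan's 117 is this value rounded down (118 if rounded up). The difference is rounding and is not pursued.

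**Expected completers at 15% shedding.** 200 × 0.85 = 170 and 100 × 0.85 = 85, together 255.

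**Three readings of pairs:**

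| Reading | Enrolled: planned against minimum | Completing: expected against minimum | Met? |
|---|---|---|---|
| Per group, one-to-one | 100 controls against 117 (17 short) | 85 controls against 100 (15 short) | No |
| Total headcount | 300 against 2 × 117 = 234 | 255 against 2 × 100 = 200 | Yes |
| Equal information | 133.3 against 117 | 113.3 against 100 | Yes |

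The last row uses the number of equal pairs that carries the same information on a difference in means, assuming equal variances: n_eq = 2/(1/n1 + 1/n2).

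- 200:100 gives 2/(1/200 + 1/100) = 133.3.
- 170:85 gives 2/(1/170 + 1/85) = 113.3.
- At 25% shedding, 150:75 gives 2/(1/150 + 1/75) = 100.0. Shedding would have to reach 25% before the trial carried no more information than 100 equal pairs.

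**For scale only.** Keeping 2:1 with 117 controls would mean 117 + 234 = 351 patients, 51 more than planned.

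**Precision.** Section X.2 plans a t test on change scores. The detectable standardised difference is (1.960 + z_power) × √(1/n1 + 1/n2). It is unadjusted and assumes equal variances and a two-sided 0.05 level; the plan gives the 0.05 threshold but not its sidedness.

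- 170:85: √(1/170 + 1/85) = 0.1328. At 80% power, 2.802 × 0.1328 = 0.372 SD. At 90%, 3.242 × 0.1328 = 0.431 SD.
- 100:100: √(1/100 + 1/100) = 0.1414. At 80% power, 2.802 × 0.1414 = 0.396 SD.

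The expected completers at 2:1 therefore give slightly better precision than 100 completers per arm.

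**The case against.** The strongest reply is that pairs was never meant per arm. Section 5.1 attaches the word to the study sample as a whole and fixes 300 before mentioning the split. On that reading the minimum is 234 patients and 300 exceeds it comfortably. The equal-information reading is also satisfied. This reply stands as far as it goes: the shortfall exists on one reading only. But both rescuing readings need a conversion that the plan does not make, and the reading that fails is the ordinary one.

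A second reply is that last-observation filling keeps dropouts in the full analysis set, so up to 100 controls enter that analysis rather than 85. That is true, and 85 should not be presented as the size of an analysis set. Nor is it the per-protocol size, because elimination and the other per-protocol conditions come on top of shedding. Even so, the plan's own step from 100 to 117 only makes sense if 100 is a target after dropout, so 85 against 100 is the comparison it invites. The enrolment gap of 100 against 117 is unaffected.

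A reader might also infer that the trial is underpowered, or that it must enrol 351. The documents support neither. No power target is stated, 170:85 carries more information than 100 equal pairs, and 351 would follow only if the cited rule binds per group, which cannot be determined from the documents.

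**Conclusion.** The point holds as a minor one. On the ordinary per-group meaning of pairs, Section 5.1 states two minimums that its own allocation misses: by 17 controls at enrolment, and by about 15 after the assumed 15% shedding. On a total or equal-information meaning both are met, but the plan states neither. What is established is a size justification that does not match the allocation beside it, not a demonstrated loss of power.

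The shortfall figures rest on the plan's 15% shedding applying equally in both arms. The information and precision figures also rest on equal variances and, for precision, on an assumed two-sided test. What the cited regulation requires remains open.

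**What to change.** Restate the 100-pair and 117-pair sentences together. Changing only the second would leave a floor of 100 pairs standing beside 85 expected control completers.

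- **If a total is meant**, suggested wording: *The minimum of 100 pairs is 200 patients in total, or about 235 after 15% shedding; 300 are enrolled at 2:1 (200:100), with about 170 and 85 expected to complete.* (200/0.85 = 235.3; the plan's truncated 117 gives 234.)
- **If per group is meant**, withdraw the claim that the 100-pair and 117-pair minimums are met. Say openly that about 170 and 85 are expected to complete, that the control arm is therefore below 100, and that 2:1 is kept to limit placebo use.
- **Optional on either reading:** add that 170:85 carries the information of about 113 equal pairs and, for a two-sided 0.05 t test on HAMD-24 change as planned in Section X.2, detects about 0.37 SD at 80% power, assuming equal variances.

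The cost is rewording one paragraph, with no change to enrolment, ratio, blinding or drug supply, provided the cited regulatory minimum does not bind per group. The sponsor has to confirm that. If it does bind, wording alone will not be enough, and the minimum and the arm sizes must be made to agree. Whether the plan should also state a target HAMD-24 difference and its SD is a separate matter and not part of this fix.
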